8.3.3 Follow-up of Adverse Events and Serious Adverse Events

AEs are recorded and assessed continuously throughout the study, as specified in [Section 8.3.1](#) (Time Period and Frequency for Collecting Adverse Event and Serious Adverse Event Information) and are assessed for their outcome at the End of Study Visit. All SAEs ongoing at the End of Study Visit must be monitored and followed up by the Investigator until stabilization or until the outcome is known, unless the participant is documented as "lost to follow-up". Reasonable attempts to obtain this information must be made and documented. It is also the responsibility of the Investigator to ensure that any necessary additional therapeutic measures and follow-up procedures are performed. Further information on follow-up procedures is given in [Appendix 3](#) (Adverse Events: Definitions and Procedures for Recording, Evaluating, Follow-up, and Reports).

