9.4.2 General Considerations

Descriptive Statistics

For the continuous parameters, the following statistics will be presented: Number (N) of participants, mean, standard deviation (SD), median, first quartile (q1), third quartile (q3), minimum, and maximum. The number of participants with missing values ('Missing') will be presented based on observed case data if necessary. An overall column will also be added where appropriate.

For categorical parameters, the total number ('N') of participants and percentages will be presented. The number of participants with missing values ('Missing') will be presented based on observed case data if necessary. An overall column will also be added where appropriate.

Method for handling missing data

Normally, missing data will not be imputed. If the participant does not have the required evidence for ovulation, follicular development, or pregnancy, then the participant will be counted as a failure for that particular endpoint.

Should a specific endpoint need another method to handle missing data, this will be specified in the Statistical Analysis Plan.

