After about 13 to 15 days of ET, early detection of pregnancy will be done by measuring β - β -hCG levels using blood tests and the results will be recorded.

The following data will be collected:

- Date of pregnancy assessment
- β -hCG test results (positive or negative)
- Details of luteal phase bleeding, if any
- Recording of AEs
- Concomitant medications prescribed and reasons.

If the result of the pregnancy assessment is negative, procedures related to End of Study visit will be performed.

Visit 5 (Clinical Pregnancy Assessment)

If the result of the β -hCG pregnancy assessment is positive, it will be further confirmed by a clinical pregnancy assessment (by means of an ultrasound examination) 4 to 6 weeks after ET.

The following data will be collected:

- Date of pregnancy assessment
- Pregnancy status
- Positive pregnancy status has to be confirmed by ultrasound examination (presence or non-presence of gestational sac(s), gestational sacs with or without heartbeat, gestational stage at which ultrasound is performed is to be recorded and ectopic pregnancy).
- Details of vaginal bleeding, if any
- Recording of all AEs, expedited reporting of all SAEs

- Concomitant medications prescribed and reasons.

If the result of the pregnancy assessment is negative, procedures related to End of Study visit will be performed.

Visit 6 (Ongoing Pregnancy assessment)

Ongoing pregnancy is defined as the presence of viable intra uterine fetus detected by ultrasound examination in 12 weeks of pregnancy. The following data will be collected:

- End of study intervention date
- Singleton pregnancy / multiple pregnancy
- Status of ongoing pregnancy
- Early miscarriage, if any
- Details of vaginal bleeding, if any
- Recording of AEs
- Concomitant medications prescribed and reasons.

If the status of ongoing pregnancy is confirmed negative, all procedures related to End of Study Visit will be performed.

If the status of ongoing pregnancy is negative and if it is due to an abortion - the reason for abortion should be recorded.

End of Study

The date and the reason of the completion/withdraw from study intervention or study (see [Section 7.2](#)) will be collected.

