## 7 Changes to the Planned Analyses in the Clinical Study Protocol

Protocol	IAP	
Original	Change	Rationale
• The CI for the difference between the two treatment groups will be calculated with the Pearson chi-square test	The CI for the difference between the two treatment groups will be calculated with the stratified "Miettinen-Nurminen" method	There is stratification randomization in this study, previous proposed Pearson chi-square test cannot provide the CI for stratified data, thus calculation method was changed to be stratified "Miettinen-Nurminen" method
• Early abortion was listed as safety secondary endpoint in the synopsis.	Early abortion is listed in the efficacy secondary endpoint section	Early abortion is a failure to pregnancy, so move it under the efficacy endpoint.

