**14 Efficacy Analyses**

**14.1 Primary Endpoint: Ongoing Pregnancy**

#### 14.1.1 Primary Objective: Analysis of the primary endpoint Ongoing Pregnancy

Analysis (Analysis Population)	Derivation	Statistical Analysis Methods	Missing data handling
Primary endpoint: Ongoing pregnancy assessment at 10-12 weeks of pregnancy [8-10 weeks after ET]			
Primary (ITT)	Ongoing pregnancy rate (%): =100 * number of subjects with ongoing pregnancy/number of subjects with ET cycle.	

Point estimate and 95%CI for each study intervention groups (Clopper-Pearson)

Point estimate and 90%CI for difference between two study intervention groups (stratified Miettinen & Nurminen (MN) method (see Miettinen & Nurminen, 1985))

It will be computed with the SAS® 9.4 FREQ procedure, using the riskdiff (COMMON) option in the Table statement and specified alpha=0.1. The results could be found in the ODS CommonPdiff table (method=' Summary Score')

	Missing=Failure
Supportive (PP)	

Time window: from the start date of first ET to the end of study.

Numerator: The subjects with ongoing pregnancy will be determined to be those with positive ongoing pregnancy result in the "Ongoing Pregnancy Assessment" eCRF page

Denominator: The subjects with ET cycle will be determined as those with ET date in "Embryo Transfer" eCRF page.

		

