#### 14.2 Secondary endpoint

Analysis (Analysis Population)	Derivation	Statistical Analysis Methods	Missing data handling
Secondary Endpoint: <math>\beta</math>-hCG positive			
Secondary (ITT)	$\beta$ -hCG positive rate (%): =100 * number of subjects with positive $\beta$ -hCG /number of subjects with ET cycle.	Same as method in the section 14.1.1	Next observation carried backward (NOCB). Missing assessment outcomes prior to positive pregnancy assessment outcome will be imputed to be positive. Note: imputation is only valid for those subjects with following positive assessment outcomes and carried backward. Otherwise, missing=failure.
Supportive (PP)	
 
Time window: from the start date of first ET to the end of study.
 
Numerator: The subjects with positive <math>\beta</math>-hCG will be determined to be those with positive <math>\beta</math>-hCG result in the "<math>\beta</math>-hCG Level" eCRF page at <math>\beta</math>-hCG positive assessment visit.
 
Denominator: The subjects with ET cycle will be determined as those with ET date in "Embryo Transfer" eCRF page.
 
		
Secondary Endpoint: Implantation			
Secondary (ITT)	Implantation rate (%): =100 * number of gestational sacs observed / number of embryos transferred.	Same as method in the section 14.1.1	Same as above
Supportive (PP)	
 
Time window: from the start date of first ET to the end of study.
 
Numerator: The number of gestational sacs will be obtained in the "Clinical Pregnancy Assessment" eCRF page.
 
Denominator: The number of embryos transferred will be obtained in the "Embryo Transfer" eCRF page.
 
		
Secondary Endpoint: Clinical pregnancy			
Secondary (ITT)	$\beta$ -hCG positive rate (%): =100 * number of subjects with clinical pregnancy/number of subjects with ET cycle.	Same as method in the section 14.1.1	Same as above
Supportive (PP)	
 
Time window: from the start date of first ET to the end of study.
 
		

	
 
Numerator: The subjects with clinical pregnancy will be determined to be those with positive clinical pregnancy result in the "Clinical Pregnancy Assessment" eCRF page
 
Denominator: The subjects with ET cycle will be determined as those with ET date in "Embryo Transfer" eCRF page.
 
		

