Secondary Endpoint: Early abortion			
Secondary (ITT)	Early abortion rate (%): =100 * number of subjects with Early abortion/number of subjects with clinical pregnancy.	Same as method in the section 14.1.1	Missing=not occurred
Supportive (PP)	
 
Time window: from the start date of first ET to the end of study.
 
Numerator: The subjects with Early abortion will be determined to be those with early miscarriage date in "early miscarriage" eCRF page.
 
Denominator: The subjects with clinical pregnancy will be determined to be those with positive clinical pregnancy result in the "Clinical Pregnancy Assessment" eCRF page.
 
		

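### Early abortion: a woman lost after a positive Visit 5 counts as abortion-free in SAP 14.2 and as a failure in the primary analysis, with no sensitivity analysis and no exit status required

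*SAP*

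**What the plan says.** SAP 14.1.1 analyses ongoing pregnancy over all women with an embryo transfer (ET) date under "Missing=Failure". For β-hCG positivity, implantation and clinical pregnancy, SAP 14.2 carries a later positive result backward. "Otherwise, missing=failure" applies to the rest.

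Early abortion follows a different rule. The rate is "number of subjects with Early abortion/number of subjects with clinical pregnancy", the numerator needs a date on the early-miscarriage eCRF page, and the missing-data rule is "Missing=not occurred". SAP 15.2.3 uses that same rule for luteal phase and vaginal bleeding, over all women with an ET date. SAP 7 reclassifies early abortion as efficacy on the ground that "Early abortion is a failure to pregnancy, so move it under the efficacy endpoint".

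On collection, Protocol Appendix 4 lists early miscarriage under Visit 6, luteal phase bleeding under Visit 4 and vaginal bleeding under Visits 5 and 6. Its End of Study entry names "The date and the reason of the completion/withdraw from study intervention or study". The Schedule of Activities has no End of Study column, although Protocol 8.3.1 closes AE collection at that visit and 8.3.3 says AEs "are assessed for their outcome at the End of Study Visit".

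**The concern.** Take a woman with a positive clinical pregnancy result at Visit 5 who is lost before Visit 6 and has no miscarriage date. In the primary she has no ongoing pregnancy. In the early-abortion analysis she stays in the denominator and is scored as having had no loss. The two analyses resolve the same missing outcome in opposite directions.

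The plan gives no reason for this choice and no sensitivity analysis around it. The exit procedures do not require the status that would resolve it. Nor does the SAP say that a miscarriage or bleed known only from AE or SAE records enters the endpoint numerators.

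A 90% confidence interval for the difference between arms is planned for early abortion and for both bleeding endpoints. If loss differs between arms, these comparisons carry the distortion. Unequal loss is possible here: the trial is open-label, and only the combination arm has a second drug to buy (Protocol 6.4).

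**Working it through.** The plan states no figure on this point, so there is none to reproduce. The check is the arithmetic of the rule.

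**Inputs from the documents**
- 334 women randomised 1:1 (Protocol 4.1, 6.3.1): 334/2 = 167 per arm.
- Clinical pregnancy 40% (Protocol 4.3): 167 × 0.40 ≈ 67 per arm.
- Clinical pregnancy 61.8% for Day 5 transfers (rationale for Protocol Version 2.0): 167 × 0.618 ≈ 103 per arm.

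**Assumptions** (the visible text gives no figure for either)
- True early-abortion risk *a*: 15%, range 10-20%.
- Share *l* lost after a positive Visit 5 with no miscarriage date: 5%, range 2-10%, unrelated to outcome.
- Every clinical pregnancy that does not end in early abortion is ongoing.

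**Formulas**, with *C* women per arm in clinical pregnancy
- Early abortion under the SAP rule: *a*(1 − *l*)
- Among women with known outcome: *a*
- All lost women counted as losses: *a*(1 − *l*) + *l*
- Ongoing pregnancy as scored: *C*(1 − *l*)(1 − *a*)/167

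**Results at *a* = 15%.** With complete follow-up, ongoing pregnancy would be 67 × 0.85/167 = 34.1% or 103 × 0.85/167 = 52.4%.

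| Loss *l* | SAP rule | Known outcome | All lost = loss | Ongoing, *C* = 67 | Ongoing, *C* = 103 |
|---|---|---|---|---|---|
| 2% | 14.7% | 15.0% | 16.7% | 33.4% | 51.4% |
| 5% | 14.25% | 15.0% | 19.25% | 32.4% | 49.8% |
| 10% | 13.5% | 15.0% | 23.5% | 30.7% | 47.2% |

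The shortfall is *a* × *l*. It runs from 0.10 × 0.02 = 0.2 points to 0.20 × 0.10 = 2.0 points. If the lost women had some other risk *r*, the shortfall would be *r* × *l*, which lies between zero and *l*. It is never negative, so the rule can only lower the rate.

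**Unequal loss, 2% versus 10%, equal 15% risk**
- Early abortion, SAP rule: 14.7% versus 13.5%. The arm losing more women looks 1.2 points better.
- All lost counted as losses: 16.7% versus 23.5%. That arm looks 6.8 points worse.
- Primary: 67 × 0.85 × 0.08/167 = 2.7 points worse, or 103 × 0.85 × 0.08/167 = 4.2 points worse.

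**Sampling error for scale.** The 90% half-width for a difference at 15% risk is 1.645 × √(2 × 0.15 × 0.85/*C*), about 8 points at *C* = 103 and 10 points at *C* = 67.

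**Bleeding.** The same formula applies, with *l* the share of women with ET who have no record. At an assumed true rate of 20%, the SAP rule gives 19.6%, 19.0% and 18.0% for 2%, 5% and 10% lost, against upper bounds of 21.6%, 24.0% and 28.0%. Vaginal bleeding has a further feature. β-hCG-negative women go to End of Study at Visit 4, so they have no Visit 5 or 6 assessment, yet they stay in the denominator. If half of women were β-hCG positive and 20% of those bled (both assumed), the rate per ET cycle would be 0.50 × 0.20 = 10%.

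**The case against.** The strongest defence is that these events have other routes into the database. AEs are collected from Visit 2 to the End of Study Visit, and their outcome is assessed there. Any spontaneous abortion is an SAE (Appendix 3), recorded vaginal bleeding after the pregnancy test is an AE (Protocol 9.4.1.2), and data before withdrawal of consent are kept. A reader might infer from the End of Study list that nothing but a date and reason is collected at exit. The documents do not support that. What stands is narrower: the list requires no pregnancy, miscarriage or bleeding status, and the SAP does not link AE/SAE records to these numerators. The AE tables are also based on events up to the last dose (SAP 15.1), so a later loss could fall outside them.

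A reader might also infer that women leave mainly because of bleeding or loss. The documents do not say so. Protocol 6.5.1 keeps women who use rescue medicine for threatened abortion in the study, and 7.2 treats a stopped fetal heartbeat as completion, a known outcome.

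The defence can add that the protocol's failure rule ("then the participant will be counted as a failure for that particular endpoint") concerns missing evidence of ovulation, follicular development or pregnancy, and that the protocol lets the SAP set other rules. Scoring every unobserved outcome as a miscarriage would be crude as a main analysis. That is fair, and it is why the all-lost figure serves here only as a bound. The SAP also tabulates discontinuations by arm and reason (10.1) and by default shows missing values as a separate category (9). Neither changes how the early-abortion rate is computed.

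**Conclusion.** The inconsistency is real on the text, and its likely size is modest. For early abortion it affects only women lost after a positive Visit 5 with no miscarriage date. Women lost before Visit 5 with no positive clinical pregnancy result are outside the denominator, so it would be wrong to read the rule as making everyone who leaves early abortion-free.

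Equal loss lowers both arms alike. One arm is favoured only if loss differs, and even the 1.2-point example is small beside a half-width of 8-10 points. A reader might place several unknown outcomes in one arm, score them all as losses, and infer a gap of about five points in the SAP result. That does not follow: with 15 recorded losses among 103 women in each arm, the SAP reports 15/103 = 14.6% in both, whichever arm holds the unknowns.

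All sizes rest on assumed loss and abortion rates, and the trial is an exploratory pilot with no confirmatory test. The point is worth acting on because the bias has a fixed direction, nothing planned would show its size, and the remedy is cheap.

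**What to change.** 1. **Protocol Appendix 4, End of Study.** For every woman leaving after ET, record pregnancy status, any miscarriage date and bleeding since the last visit at the existing End of Study contact. Add that contact to the Schedule of Activities.
2. **SAP 14.2, early abortion.** Report the rate among women with clinical pregnancy who have a known Visit 6 status or a recorded loss. Take losses from both the early-miscarriage page and the SAE records, and state how the two are reconciled. Add a bound that counts missing outcomes as losses.
3. **SAP 15.2.3, bleeding.** Show the number not assessed, by arm. For vaginal bleeding, keep the rate per ET cycle and add the rate among β-hCG-positive women with a completed Visit 5 or 6 assessment or a recorded bleeding event. Restricting the numerator to completed assessments without changing the denominator would leave all β-hCG-negative women unassessed. This table needs an edit anyway: it labels the two pregnancy assessments Visits 6 and 7, where the current protocol has Visits 5 and 6.

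The cost is protocol and SAP wording, a few exit data items, extra table rows and a slightly smaller early-abortion denominator.

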## 15 Safety Analyses

The subsections in this section include specifications for summarizing safety endpoints that are common across clinical studies such as adverse events, laboratory tests and vital signs.

Safety analyses will be done on the safety analysis population and according to the as-treated principle.

### 15.1 Adverse Events

Unless otherwise stated AE will be assessed via summary statistics.

#### Definitions

**Treatment-emergent adverse events (TEAEs):** those events with onset dates occurring within the treatment periods. The **treatment period** is defined from the first day of study intervention after randomization until last dose of study intervention date or the clinical cut-off date, whatever occurs earlier.

All analyses described in Section 15.1 will be based on TEAEs if not otherwise specified.

Adverse events **related to study intervention** are those events with relationship missing, unknown or yes.

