4.1 Overall Design

This is a Phase IV, local, single center, open label, pilot, randomized controlled clinical study to compare the efficacy and safety of Crinone® versus combination medication. The study population are infertile women who receive FET in ACs. This study plans on including 334 participants from a single reproductive center over 25 months. Participants that enter the study will be randomized into either of the two groups. The study intervention drug received by the participant is determined based on the result of randomization. The randomization procedure is described in [Section 6.3](#). The overall scheme of the study is in [Section 1.2](#) and the Schedule of Activities at each visit can be found in [Section 1.3](#).

The participants will sign an ICF; the participants are free to withdraw at any time without prejudice to their medical care, and they are not obliged to state their reasons for withdrawal. Upon site initiation, the Investigator site will enroll the eligible participants who meet the inclusion and none of the exclusion criteria in a consecutive manner until the enrollment target is reached. The study will consist of a screening period, followed closely by procedures from endometrial transformation to ongoing pregnancy assessment, which lasts for approximately 75 days. Study treatment will start from the day of endometrial transformation (Day -5) until ongoing pregnancy assessment, which occurs between 10-12 weeks of pregnancy (8-10 weeks after ET). The middle number of 9 weeks (Day 63) after ET is used to define the study day with a window of 10 days on each side as leeway. The treatment will be administered for approximately 75 days.

Relevant data according to study requirements will be recorded in standard CRF. When the study starts, this reproductive center will include participants who enter the cycle. The information of the qualified yet excluded participants who have signed ICFs will be recorded, and the reason for their exclusion will also be recorded in the CRF. If a participant has entered the study and later discontinue their study intervention, the reason for discontinuing the study intervention will be recorded in the CRF.

[figure not shown]
Participant follow-up will occur until her ongoing pregnancy is confirmed and/or until End of Study (defined in [Section 4.4](#)).

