6.1 Study Interventions Administration

Study Intervention Name:	Crinone®	Duphaston®
Dose Formulation:	Progesterone gel 8% (90 mg)	Tablet
Unit Dose Strength(s)/Dosage Level(s):	90 mg	10 mg/tablet
Route of Administration:	Intravaginal	Oral
Dosing Instructions:	1 gel, q.d. in the morning	1 tablet, b.i.d
Supplier/Manufacturer:	Merck will provide Crinone® for free	Prescribed for participants in the clinic by Investigators
Packaging and Labeling	
every box contains 15 applicatorsThe validity period is 36 monthsEach applicator will be packaged and labeled per all applicable regulatory requirements and Good Manufacturing Practice Guidelines.	
According to the package labelling as prescribed by the Investigator

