8.3 Adverse Events and Serious Adverse Events

The definitions of an AE and a SAE are in [Appendix 3](#).

8.3.1 Time Period and Frequency for Collecting Adverse Event and Serious Adverse Event Information

The AE reporting period for safety surveillance begins upon endometrial transformation (Visit 2) and continues until the End of Study Visit.

Any SAE assessed as related to study intervention must be recorded and reported, as indicated in [Appendix 3](#), whenever it occurs, irrespective of the time elapsed since the last administration of study intervention.

The method of recording, evaluating, and assessing causality of AEs (including SAEs) and the procedures for completing and transmitting SAE reports are in [Appendix 3](#).

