9.3 Populations for Analyses

The analysis populations are specified below. The final decision to exclude participants from any analysis population will be made during a data review meeting prior to database lock.

Analysis Set	Description
Intention-to-Treat (ITT)	The ITT Population will include all participants who receive at least one dose of randomized study intervention. Participants will be analyzed according to the study intervention they were initially assigned.
Per-Protocol (PP)	Includes all participants in ITT population without any major protocol violations.
Safety Population	Include all participants who have received at least one dose of study intervention. Participants will be analyzed according to the actual study intervention they received

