- Gynecological history: duration of infertility, menstrual cycle, history of miscarriages, history of pelvic surgery, history of ovarian surgery.
- Medical history and concomitant illness
- Any concomitant medication taken by the participant when entering the study
- Concomitant medications prescribed and reasons
- Ultrasound without abnormal findings (endometrium thickness will be measured); examinations from medical history prior to the initiation of estradiol valerate before signing the ICF is also accepted per the Investigators decision
- Serum β -hCG levels must be negative; examinations from medical history prior to signing the ICF is also accepted per the Investigators decision
- Check I/E criteria
- Date of initiation of estradiol valerate (if applicable)
- Initial dose of estradiol valerate (if applicable)
- Details of dose adjustments of estradiol valerate if any (if applicable)
- Duration and total dosage of estradiol valerate (if applicable)

Visit 2 (endometrial transformation day)

The participants should come to the clinic to measure their endometrial thickness on endometrial transformation day. Should the endometrial thickness be ≥ 8 mm, Crinone® will be administered at a dose of 90 mg/d for 4-6 days to assist the secretory transformation of the endometrium. The following data will be collected:

- Date of initiation of estradiol valerate
- Initial dose of estradiol valerate
- Details of dose adjustments of estradiol valerate if any
- Duration and total dosage of estradiol valerate
- Date of initiation of Crinone®

- Endometrial thickness before initiation of Crinone® (Endometrial thickness will be measured by ultrasound. However, if the ultrasound was performed on the endometrial transformation day prior to signing the ICF, a new ultrasound is not required.)
- Check I/E criteria
- Recording of AEs
- Concomitant medications prescribed and reasons.

The total duration of estradiol valerate before the endometrial transformation should be no more than 20 days.

Visit 3 (embryo transfer day)

After 4-6 days of assisted secretory transformation of the endometrium, no more than two D5 embryos will be transferred on the fifth, sixth, or seventh day. After randomization, the luteal phase support study intervention will be initiated.

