- Study intervention A (Crinone® group): Randomized participants will be given Progesterone gel 8% (Crinone®) 90 mg/p.v./q.d from the day of endometrial transformation. It will be suggested that they administer the drug in the morning and at the same time of day throughout the trial. A β -hCG test will be done 14 days after ET. If serum β -hCG levels are negative, the study will be discontinued. If the result of the β -hCG test is positive, Crinone® administration will continue with the above regimen. At 35 days after ET, an ultrasound will be done to detect the number of gestational sacs to confirm the results of clinical pregnancy. If clinical pregnancy is positive, continue Crinone® administration until ongoing pregnancy assessment. Should a miscarriage occur at any point, Crinone® administration will be discontinued.
- Study intervention B (Crinone® + Duphaston® group): Randomized participants will be given Progesterone gel 8% (Crinone®) 90 mg/p.v./q.d from the day of endometrial transformation, following which Duphaston® at 10 mg/p.o./bid will be administered from the day of ET. It will be suggested that they administer the drugs in the morning and at the same time of day throughout the trial. A β -hCG test will be done 14 days after ET. If serum β -hCG levels are negative, the study will be discontinued. If the result of the β -hCG test is positive, the combination medication will continue with the above regimen. At 35 days after ET, an ultrasound will be done to detect the number of gestational sacs to confirm the results of clinical pregnancy. If clinical pregnancy is positive, continue combination medication until ongoing pregnancy assessment. Should a miscarriage occur at any point, combination medication will be discontinued.

All participants will receive oral estradiol valerate continuously and the dose of estradiol valerate will be adjusted according to local practices.

The following data will be collected:

- Duration and total dosage of estradiol valerate

- Date of ET
- Number of embryo(s) transferred (no more than 2)
- Embryo quality
- Check I/E criteria
- Recording of AEs
- Concomitant medications prescribed and reasons.

Visit 4 (β -hCG positive assessment)

Participants treated by ART are routinely monitored for early detection of pregnancy by measuring serum β -hCG concentration according to the site's routine clinical practices.

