## **Time window**

Day 1 is the day of start of study intervention after randomization, the day before is Day -1 (no Day 0 is defined).

Study day is defined relative to Day 1.

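### Adverse events with a dated onset in the 4-6 day Crinone run-in reach no AE table specified in the SAP, a narrowing it does not declare, and the SAP does not settle whether ET day is Day 1

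*SAP*

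**What the plan says.** **Protocol.** Section 4.1: "Study treatment will start from the day of endometrial transformation (Day -5) until ongoing pregnancy assessment". Appendix 4 (Visit 2) says that Crinone "will be administered at a dose of 90 mg/d for 4-6 days to assist the secretory transformation of the endometrium". Section 6.3.1 and the Schedule of Activities place randomisation on ET day, which the schedule calls Day 1. Crinone is dosed "1 gel, q.d. in the morning" (6.1). In the combination arm Crinone comes first, "following which Duphaston® at 10 mg/p.o./bid will be administered from the day of ET" (Appendix 4, Visit 3).

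AE collection starts with the run-in. Section 8.3.1 reads: "The AE reporting period for safety surveillance begins upon endometrial transformation (Visit 2", and it runs to the End of Study Visit. Section 9.4.1.3 makes the incidence and severity of every AE the safety parameter. Section 9.3 defines the Safety Population as: "Include all participants who have received at least one dose of study intervention".

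**SAP.** The treatment period in 15.1 "is defined from the first day of study intervention after randomization until last dose of study intervention date or the clinical cut-off date", and the analyses in 15.1 use treatment-emergent events (TEAEs) unless stated otherwise. In section 9, "Day 1 is the day of start of study intervention after randomization". Section 8.2 adds a post-randomisation condition to the Safety Population. The safety timeframe in section 5 and the exposure start in section 13 carry the same limit; section 13 acknowledges that Crinone is given before randomisation. Section 7 lists two changes from the protocol, and this is not one of them.

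**The concern.** The protocol treats the run-in gel as study treatment and collects AEs during it, but the SAP gives those events no place in the AE tables. A reaction that begins on Crinone before transfer is not counted, even if it persists after randomisation or is the reason for stopping. A woman who stops before randomisation is outside the safety set altogether. The run-in is also the only period in which women later assigned to the combination take Crinone without Duphaston. That matters in a plan that tabulates events related to Crinone only (SAP 15.1.1).

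The second issue is the anchor. The protocol fixes Day 1 as ET day for everyone. The SAP ties Day 1 to the first dose after randomisation, and the two arms have different drugs due on that day: a once-daily morning gel in one, and the gel plus newly started Duphaston in the other. If the rule is not pinned down, the start of the AE window depends on the programmer's reading, on the day of the transfer procedure.

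**Working it through.** **1. Run-in length.** The schedule puts endometrial transformation at Day -5 with a window of ±1, and ET at Day 1. With no Day 0 (SAP 9), the run-in is 4, 5 or 6 days and ET falls on the fifth, sixth or seventh day. This reproduces Appendix 4. The stated treatment length of about 75 days is also reproduced: 5 run-in days + 70 days (10 weeks after ET) = 75.

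**2. Tracing a run-in event.** Take an AE with a recorded onset on Day -3.
- Protocol: collected (8.3.1), within the safety endpoint (9.4.1.3), and in a woman who belongs to the Safety Population (9.3).
- SAP 15.1.1: excluded, because onset precedes the treatment period. Some rows are labelled AE rather than TEAE, but the default rule still applies to them.
- SAP 15.1.2 (AEs leading to discontinuation): same default, so excluded.
- SAP 15.2.2 (SAEs): refers back to 15.1.1, so excluded.
- If the woman stopped before randomisation, SAP 8.2 also removes her from the safety set. SAP 10.1 counts her only under her main reason for discontinuing.

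One exception: under SAP 15.1 a missing onset, or a partial one matching the start month or year, can be moved to the start of study intervention. That text does not say whether the start is the first run-in dose or the first dose after randomisation. The exclusion is therefore certain only for events with a known onset date.

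**3. How much follow-up is left out.** For 334 women (Protocol 4.1), each completing the run-in:
- 334 × 5 = 1,670 participant-days; range 334 × 4 = 1,336 to 334 × 6 = 2,004.
- Woman followed to Day 63: 5/(5+63) = 7.4%; range 4/(4+73) = 5.2% to 6/(6+53) = 10.2%.
- Woman stopping at a negative β-hCG test on Day 14: 5/(5+14) = 26%; range 4/(4+15) = 21% to 6/(6+13) = 32%.

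**4. Where the window starts.** Duphaston begins on Day 1. The documents do not give the clock time of randomisation relative to that day's gel.

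| Reading of the SAP rule | Crinone arm | Combination arm | Lag |
|---|---|---|---|
| Dose date on or after randomisation date | Day 1 | Day 1 | 0 |
| Dose date strictly after randomisation date | Day 2 | Day 2 | 0 |
| Clock time, ET-day gel after randomisation | Day 1 | Day 1 | 0 |
| Clock time, ET-day gel before randomisation | Day 2 | Day 1 | 1 day |

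The arms differ under one reading, by one day: 1/63 = 1.6% of the window to Day 63, or 1/14 = 7.1% for a woman who stops at Day 14. The second reading loses ET day in both arms and conflicts with the protocol schedule. Luteal phase bleeding is anchored on ET and vaginal bleeding on the β-hCG visit (SAP 15.2.3), so neither rate moves under any reading.

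**The case against.** **The safety objective is comparative, and the run-in is not.** The run-in precedes randomisation and is shared, so leaving it out cannot by itself bias the comparison. SAP 5 states the post-randomisation timeframe openly. Taken literally, the protocol's population, analysed by treatment actually received, would put never-randomised women in the Crinone column. All of this stands. It supports keeping the comparative tables post-randomisation. It does not justify having no run-in table at all, or leaving the change out of SAP 7.

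**The events are not wholly invisible.** Pre-randomisation discontinuations are counted by main reason in SAP 10.1, and SAE reporting to the sponsor is unaffected. Both points are right, but neither is an AE summary.

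**A reader might infer that the two arms' windows do start on different days and that Crinone alone will look safer.** The documents do not support that. It needs the rule to be judged by clock time and the ET-day gel to precede randomisation, and neither is stated. The SAP speaks of first days and dose dates throughout, which points to date-level handling with no lag. Protocol 6.1 instructs morning dosing, but Appendix 4 only suggests it. Nor can a size be given. If a fraction r of women had their only TEAE begin on ET day, and a fraction q of the Crinone arm used the gel before randomisation, the artificial difference would be r × q. With assumed r of 1% to 10% and q of 50% to 100%, that is 0.5 to 10 percentage points, but the documents give neither quantity.

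**A reader might also infer that the run-in is each woman's first exposure to the gel.** It is her first exposure in this study. Women with up to two failed transfer cycles are eligible, and nothing requires them to be new to Crinone.

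**Conclusion.** The run-in part holds on the text alone. The SAP narrows the Safety Population and the TEAE window to the period after randomisation, contrary to Protocol 8.3.1, 9.3 and 9.4.1.3, without declaring it. Dated run-in AEs, from about 1,670 participant-days (1,336 to 2,004), are therefore collected but not tabulated. The figure assumes that 334 women complete the run-in; women who stop during it are additional if 334 counts only those randomised. The consequence is lost Crinone safety information, with no demonstrated bias between arms.

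The window start on ET day is an ambiguity. It is worth at most one day between arms, under one of four readings, and its effect on AE rates is unknown. The primary endpoint and both bleeding rates are unaffected. The sponsor should correct both before database lock.

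**What to change.** 1. In SAP 9 and 15.1, set Day 1 and the start of the comparative treatment period to the ET/randomisation date in both arms, as in the protocol schedule. State that this is decided by calendar date, and name the start date used when AE onset is imputed.
2. Add one table, pooled across arms, of AEs with onset from the first Crinone dose up to ET, in all women given at least one dose, including those never randomised. Add a matching SAE listing. State on which side of the boundary an ET-day onset falls, so that each event is counted once.
3. Reconcile the Safety Population in SAP 8.2 with Protocol 9.3 and list the change, with its reason, in SAP 7. Keeping the post-randomisation set for the comparative tables is reasonable once declared.

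Cost: SAP wording, one table and one listing. AE collection already starts at Visit 2, so no new data are needed.
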